Sixty-four patients with pancreatic cancer have been treated with AM0010 in monotherapy or in combination with chemotherapy. One patient receiving AM0010 5 µg/kg with FOLFOX experienced Grade 2 gastric hemorrhage and 1 patient on AM0010 5 µg/kg with gemcitabine/paclitaxel experienced Grade 3 gastrointestinal hemorrhage.

Pancreatic cancer patients have a high incidence of thrombosis. Anticoagulants with a $t_{1/2}$ of less than 24 hours are frequently prescribed in this patient population and were allowed for patients with pancreatic cancer on the Phase 1 study. The use of anti-coagulant did not lead to bleeding events in AM0010-treated patients.

To avoid Grades 3–4 hematological toxicity and dose interruptions, intermittent dosing schedules were modeled to understand the decline and rapid recovery of platelets during AM0010 therapy. The AM0010 dosing schedule selected for the Phase 3 study, 5 days on, 2 days off, is predicted to avoid Grade 3 and 4 thrombocytopenia in advanced cancer patients receiving AM0010 in combination with FOLFOX without compromising the immune stimulatory mechanism of action of AM0010.

In the Phase 1 study with AM0010, 36 patients were on Low Molecular Weight Heparin (LMWH), 6 patients were on an oral factor Xa inhibitor, and 9 patients were on low-dose warfarin for IV port maintenance, with no major bleeding events reported.

In addition, the Phase 3 study will exclude patients on Coumadin. For patients who wish to participate, the prescription will be changed to a Factor II or Xa inhibitor with a $t_{1/2}$ of less than 24 hours or LMWH.

In summary, these data indicate that AM0010 alone and in combination with chemotherapy induces thrombocytopenia that is manageable in patients with advanced solid malignancies. CCI

CCI

1.3 AM0010 Dose Rationale

1.3.1 Clinical Experience with AM0010

In a previous First-in-Human study, preliminary exposure and safety and efficacy data have been collected.

The previous dose escalation study defined the safety profile, maximum tolerated dose, recommended Phase 3 dose as monotherapy and in combination with chemotherapy, PK, and objective tumor responses (according to immune-related response criteria) in patients with advanced solid malignancies.

In the previous studies, 33 patients with advanced solid malignancies across several indications (melanoma, ovarian, pancreatic, prostate, renal cell, colorectal, and non-small cell lung carcinoma [NSCLC]) were exposed to AM0010 as a single agent. Patients received doses from 1 µg/kg up to 40 µg/kg daily. Cohorts 1 through 6 (1 through 40 µg/kg) were found to be well tolerated.

Subsequently, clinical activity was further explored in 9 dose expansion cohorts with AM0010 monotherapy in specific disease indications such as cholangiocarcinoma, renal cell carcinoma (RCC), colorectal cancer (CRC), NSCLC, and PDAC. Efficacy of AM0010 in combination with chemotherapy, targeted therapy, or immune checkpoint inhibitors was explored in 9 additional combination regimens (Table 8).

CCI

The image shows the letters 'CCI' in a large, bold, orange font. The 'C's are stylized with a gap at the top, and the 'I' is a simple vertical bar. The letters are set against a solid black background.

Most patients enrolled in the escalation cohorts and first expansion cohort had previously progressed during or following multiple lines of therapy. Despite this fact, very encouraging objective tumor responses have been observed in most combination therapies with AM0010.

1.3.2 AM0010 Dose Rationale for Pancreatic Cancer with FOLFOX

The safety, tolerability, and preliminary efficacy of AM0010 have been evaluated as monotherapy and in combination with chemotherapy, targeted agents, and immune checkpoint inhibitors at doses between 5 and 40 $\mu\text{g}/\text{kg}$ SQ daily. Based on the clinical experience in 353 patients as of 29 October 2017, AM0010 has a manageable safety profile in patients with advanced solid malignancies including pancreatic cancer when combined with FOLFOX. The most commonly reported AE was reversible thrombocytopenia. In a Phase 1b study, Grade 3–4 thrombocytopenia was observed in 55% of patients receiving uninterrupted daily AM0010 dosing in combination with FOLFOX. In all patients with Grade 3–4 thrombocytopenia, dose interruption led to the recovery of platelet counts within 7 days. Modeling of the platelet counts indicates that 5 days AM0010 dosing followed by 2 days rest will prevent Grade 3–4 thrombocytopenia in patients treated with the AM0010 plus

FOLFOX regimen. CCI [REDACTED]

[REDACTED]

[REDACTED]

[REDACTED]

[REDACTED]

[REDACTED]

[REDACTED]

[REDACTED]

[REDACTED]

In a Phase 1b study 21 patients with PDAC who had progressed on prior gemcitabine-based therapy, and who did not receive any prior platinum-based regimen, were enrolled in a Phase 1b expansion cohort on 5 µg/kg AM0010 plus FOLFOX. The median age of those 21 patients was 64 years (range, 43–77 years). Median number of prior therapies is 2 (range 1–5).

In this cohort, 19 patients had a tumor response assessment; 2 had an irCR, 1 had an irPR-100% reduction in measurable lesions, 11 had an irSD, and 4 had a BOR of irPD. The median follow-up period is 20.3 months (range 15.8–25.9 months).

The time on prior treatments and on this study for PDAC patients receiving AM0010 plus FOLFOX is shown in [Figure 1](#). Nine of 21 patients received more than 16 weeks of treatment. The best response for the reduction in the serum tumor marker CA 19-9 is shown in [Figure 2](#). CA 19-9 is a serum tumor marker that is elevated in approximately 60% of pancreatic cancers. Any reduction in CA 19-9 and the best response in CA 19-9 are correlated with a prolonged OS of patients with pancreatic cancer treated with a gemcitabine-based regimen ([Chiorean, Von Hoff et al. 2016](#)). In this cohort, 9 of 12 patients (75.%) had a reduction of CA 19-9, with 7 of the 9 patients having a reduction of at least 20% ([Figure 2](#)).

In all 21 patients (ITT population), the median PFS was 2.6 months and the median OS was 10.2 months. The 1-year survival was 42.9% ([Figure 3](#)).

[figure not shown]
Based on early results, a 5-µg/kg dose combined with FOLFOX is proposed for this Phase 3 trial. At this dose level, thrombocytopenia associated with the combination treatment is manageable and is associated with early evidence of efficacy.

The proposed dosing schedule (5 days on, 2 days off) is predicted from hematologic and biomarker analysis and modeling to mitigate the risk of thrombocytopenia while maintaining the activation of the immune system and clinical benefit. These findings support the selection of a 5/2 regimen to replace the daily SQ regimen administered in a previous clinical trial. This 5/2 regimen is expected to decrease the incidence and magnitude of thrombocytopenia and permit recovery of platelet counts during the 2-day off rest period.

The rationale for dosing at a flat rate with a cutoff at 80 kg is based on safety and on the PK/pharmacodynamic relationship. More specifically, immune activation with AM0010 requires a serum trough of at least 1 ng/mL. This minimal trough level is reached with actual doses of 2.5 µg/kg and higher. The maximum tolerated dose (MTD) of AM0010 monotherapy is 20 µg/kg.

In a Phase 1b study with AM0010 + FOLFOX, patients received individual weight-based doses of a median of 6.31 µg/kg AM0010 (range 4.19–9.11 µg/kg). Within this Phase 1b study, encouraging OS was observed in patients receiving more than 5 µg/kg, based on their individual weight. Safety and tolerability of AM0010 + FOLFOX was also explored in a dose escalation study, in which patients received up to 13.4 µg/kg. However, patients with doses above 10 µg/kg in combination with FOLFOX may have required dose reductions.

Table 9 provides the actual received dosage per kg for patients with weights between 40 and 160 kg. It shows that a safe and efficacious dose is obtained with the proposed flat rate dosing for patients above and below 80 kg.

AM0010 at 10 µg/kg was determined to be the optimal biologic dose for maintenance therapy. In 144 patients who received monotherapy in Phase 1 the MTD was determined to be 20 µg/kg as described in the IB. The pharmacodynamic analysis indicates immune activation at 10 µg/kg as monotherapy (Naing et al JCO, 2016). Therefore, AM0010 at 10 µg/kg was chosen for the maintenance dose.

1.3.3 Rationale for Evaluating CA 19-9

A biological marker widely used in clinical practice in the assessment and follow-up of patients with pancreatic cancer is CA 19-9. A strong correlation between marker decline during chemotherapy and patient outcomes has been observed, particularly in patients with metastatic pancreatic cancer. In the Phase 3 trial of ABI-007 in combination with gemcitabine for advanced adenocarcinoma of the pancreas, remarkable decreases of CA 19-9 were observed ([Von Hoff, Ervin et al., 2013](#)). A total of 61% in the nab-paclitaxel cohort had a decrease of at least 20% in CA 19-9. Patients with at least 90% decrease in CA 19-9 levels lived 13.5 months. In a recent publication by [Chiorean et al.](#), CA 19-9 decreases at 8 weeks are predictors of OS in a randomized Phase 3 study (MPACT) of weekly nab-paclitaxel plus gemcitabine versus gemcitabine alone in patients with metastatic pancreatic cancer ([Chiorean, Von Hoff et al., 2016](#)). Since CA 19-9 is being used only in an exploratory evaluation to determine whether there is a correlation with efficacy outcomes, increases in CA 19-9 levels in this study should not be used as evidence for progressive disease or for discontinuing patients from study treatment.

2.0 STUDY OBJECTIVES AND INVESTIGATIONAL PLAN

2.1 Study Objectives

2.1.1 Primary Objective

To compare the efficacy of AM0010 in combination with FOLFOX versus FOLFOX alone in patients with metastatic pancreatic cancer as measured by OS.

2.1.2 Secondary Objectives

The secondary objectives are:

- To compare the efficacy of AM0010 in combination with FOLFOX versus FOLFOX alone in patients with metastatic pancreatic cancer as measured by:
 - PFS
 - Objective response rate (ORR), DCR, and duration of response (DoR) by Response Evaluation Criteria in Solid Tumors (RECIST) v.1.1
 - 1-year survival rate
- To compare the safety and tolerability of AM0010 in combination with FOLFOX versus FOLFOX alone

2.1.3 Exploratory Objectives

- To explore biomarkers that may correlate with tumor response, immune activation, and relationships to clinical efficacy outcomes.
- To explore associations between patient-reported symptoms, functioning, and global health status/QoL using the European Organisation for Research and Treatment of Cancer Quality of Life Core 30-item (EORTC QLQ-C30) questionnaire as well as current health status and the EuroQoL 5-dimension (EQ-5D) Index used in the economic evaluation of health care using the EuroQoL 5-dimension 5-level (EQ-5D-5L) questionnaire.

2.2 Study Design

This is a randomized, open label, global Phase 3 Study of AM0010 in combination with FOLFOX compared with FOLFOX alone as second-line therapy in patients with advanced metastatic pancreatic cancer that has progressed during or following a first-line gemcitabine-containing regimen.

Approximately 566 patients will be randomized. Two interim analyses are planned. The first interim analysis will be performed when at least 60 randomized patients have had the opportunity to receive 4 months of therapy from the date of Randomization. Based on the first interim analysis, the Data Monitoring Committee (DMC) will review the PK exposure-safety and PK exposure-efficacy on the composite aggregate data for a Go/No-Go decision to enroll the entire Phase 3 study. The enrollment will continue during the analysis. The second interim analysis will occur when approximately 276 deaths (70% of total 393 deaths needed for final analysis) have occurred. Based on the second interim analysis, the DMC will recommend modifying, continuing the trial as planned, or discontinuing the trial.

Patients will be randomized in a 1:1 ratio to AM0010 combined with FOLFOX or FOLFOX alone.

The randomization will be stratified by 2 stratification factors:

- Prior single-agent gemcitabine therapy versus gemcitabine/nab-paclitaxel therapy
- North America versus Europe versus APAC.

Treatment Arms:

[figure not shown]
ARM 1: AM0010 (5 µg/kg) SQ dosed on Days 1–5 (with rest on Days 6 and 7) and Days 8-12 SQ (with rest on Days 13 and 14) plus FOLFOX (*dl*-LV 400 mg/m² and oxaliplatin 85 mg/m² followed by bolus 5-FU 400 mg/m² and a 46- to 48-hour infusion of 5-FU 2400 mg/m²) initiated on Day 1 of a 14-day cycle, for up to 12 cycles or until disease progression by RECIST v.1.1.

While receiving FOLFOX during Cycles 1–12, AM0010 at 5 µg/kg will be administered as 1 of 2 fixed doses, either 0.4 mg for patients weighing ≤80 kg or 0.8 mg for patients weighing >80 kg.

Patients in ARM 1 may continue on maintenance cycles with AM0010 (as shown below). After discontinuation of FOLFOX in the absence of tumor progression (ie, completion of the planned 12 cycles or unacceptable FOLFOX related toxicity), AM0010 at 10 µg/kg will be administered as 1 of 2 fixed doses, either 0.8 mg patients weighing ≤80 kg or 1.6 mg for patients weighing >80 kg.

ARM 1: AM0010 plus FOLFOX, for up to 12 cycles or until disease progression by RECIST v.1.1.

Figure 4: ARM 1: AM0010 + FOLFOX

ARM 1 in the absence of tumor progression may continue maintenance with AM0010 alone at either 0.4 mg for patients weighing ≤ 80 kg or 0.8 mg for patients weighing > 80 kg after completion of FOLFOX or FOLFOX intolerance

ARM 2: FOLFOX alone, initiated on Day 1 of a 14-day cycle, for up to 12 cycles or until disease progression by RECIST v.1.1.

Figure 5: ARM 2: FOLFOX Alone

[figure not shown]
[figure not shown]

Figure 6: Study Design Schema

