ARM 1: AM0010 (5 µg/kg) subcutaneous (SQ) dosed on Days 1–5 (with rest on Days 6 and 7) and Days 8–12 SQ (with rest on Days 13 and 14) plus a FOLFOX regimen (a 2-hour infusion of *dl*-LV 400 mg/m² and oxaliplatin 85 mg/m² followed by bolus 5-FU 400 mg/m² and a 46- to 48-hour infusion of 5-FU 2400 mg/m²) initiated on Day 1 of a 14-day cycle for up to 12 cycles or until disease progression by RECIST v.1.1.

While receiving FOLFOX during Cycles 1–12, AM0010 at 5 µg/kg will be administered as 1 of 2 fixed doses, either 0.4 mg for patients weighing ≤80 kg or 0.8 mg for patients weighing >80 kg.

Patients in ARM 1 may continue on maintenance cycles with AM0010 (as shown below). After discontinuation of FOLFOX in the absence of tumor progression (ie, completion of the planned 12 cycles or unacceptable FOLFOX related toxicity), AM0010 at 10 µg/kg will be administered as 1 of 2 fixed doses, either 0.8 mg for patients weighing ≤80 kg or 1.6 mg for patients weighing >80 kg.

ARM 1: AM0010 plus FOLFOX, for up to 12 cycles or until disease progression by RECIST v.1.1.

ARM 1: AM0010 plus FOLFOX

[figure not shown]

ARM 1 in the absence of tumor progression may continue maintenance with AM0010 alone at either 0.4 mg for patients weighing ≤ 80 kg or 0.8 mg for patients weighing > 80 kg after completion of FOLFOX or FOLFOX intolerance

ARM 2: FOLFOX alone, initiated on Day 1 of a 14-day cycle, for up to 12 cycles or until disease progression by RECIST v.1.1.

**Study Design
(continued)**

ARM 2: FOLFOX Alone

[figure not shown]

Crossover of patients from the FOLFOX-only treatment arm into the FOLFOX plus AM0010 treatment arm is not permitted.

Patients randomized to the investigational combination treatment (AM0010 plus FOLFOX) ARM 1, after completion of up to 12 cycles of combination chemotherapy or if experiencing chemotherapy intolerance (as defined as Grade 3 or 4 non-hematologic toxicity that does not resolve to baseline in 28 days with standard of care or hematologic Grade 4 toxicity that does not resolve to baseline in 28 days), may continue to receive maintenance AM0010 if the patient continues to receive clinical benefit (CR, PR, SD).

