5.1 Treatment Administration

5.1.1 AM0010

AM0010 is provided as a sterile, clear solution formulated at a concentration of 2 mg/mL and 4 mg/mL.

The AM0010 drug product is stored at the pharmacy at 2°C to 8°C. Patients will store their AM0010 in their refrigerator (2°C to 8°C).

While receiving FOLFOX during Cycles 1–12, AM0010 5 µg/kg will be administered as 1 of 2 fixed doses, either 0.4 mg for patients weighing ≤80 kg or 0.8 mg for patients weighing >80 kg.

AM0010 will be administered as a fixed dose, bracketed in 2 weight groups. Ongoing PK analysis has shown that the apparent clearance is proportional to weight supporting a weight-based dosing.

The rationale for dosing at a flat rate with a cutoff at 80 kg is based on safety and on the PK/Pharmacodynamic relationship. More specifically, immune activation with AM0010 requires a serum trough of at least 1 ng/mL. This trough level is reached with actual doses of 2.5 µg/kg and higher. The MTD of AM0010 is 20 µg/kg. Following the bracketed fixed dosing regimen, all patients will receive between 5 and 10 µg/kg AM0010. This dose range correlated with a survival benefit in a Phase 1b study with AM0010 + FOLFOX in PDAC patients.

The effects of overdose with AM0010 and an antidote to overdose with AM0010 are unknown. Non-human primates have been exposed to 5-10 times the expected serum concentration in humans without acute adverse reactions.

For any subject experiencing AM0010 overdose, observation for any symptomatic side effects should be instituted and vital signs and biochemical and hematologic parameters should be followed closely

(consistent with the protocol or more frequently, as needed). Appropriate supportive management to mitigate adverse effects should be initiated.

After discontinuation of FOLFOX (ie, completion of the planned 12 cycles or unacceptable FOLFOX-related toxicity), the AM0010 dose at the 10- $\mu\text{g}/\text{kg}$ dose level will be administered as 1 of 2 fixed doses (ie, either 0.8 mg in 0.2 mL for body weight ≤ 80 kg or 1.6 mg in 0.4 mL for body weight > 80 kg), based on the patient's weight during the course of the study.

In 144 patients who received AM0010 monotherapy, the MTD was determined at 20 $\mu\text{g}/\text{kg}$ (Naing et al., 2016). Pharmacodynamic analysis indicates immune activation at 10 $\mu\text{g}/\text{kg}$ in a monotherapy setting.

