5.1.3 Dosing Schedule

Patients will be treated on an outpatient basis with AM0010 plus FOLFOX or FOLFOX alone. Each cycle is 14 days.

ARM 1: AM0010 plus FOLFOX

[figure not shown]
AM0010 dose should be administered on Days 1–5 and Days 8–12 in the morning, ideally with 24 hours (± 2 hours) between doses. Days 6, 7, 13, and 14 will be rest days. FOLFOX dosing should be initiated on Day 1 of each cycle, after AM0010 administration on investigational ARM 1 (Figure 7). ARM 2 consists of FOLFOX administration alone as shown below, initiated on Day 1 of a 14-day cycle (Figure 8).

For patients in the combination therapy (AM0010 + FOLFOX) arm, after the last scheduled chemotherapy cycle in the absence of tumor progression, up to 12 cycles, or chemotherapy intolerance, maintenance dosing of AM0010 may continue 5 days on and 2 days off at 10 $\mu\text{g}/\text{kg}$ SQ qd (see Section 5.1.1).

Crossover of patients from the FOLFOX-only treatment arm into the FOLFOX plus AM0010 treatment arm is not permitted. Supportive care per the institution's normal standard of care, including concomitant medications, can be provided at the Investigator's discretion.

[figure not shown]
The documentation of the investigational product administration will be noted on the CRF page and in the source documentation. The date, dose volume, and time of administration for each dose will be recorded in the patient diary and on the respective CRF page. Details of preparing and administering AM0010 will be provided to the patient and are included in the Pharmacy Manual.

Figure 7: ARM 1: AM0010 + FOLFOX

ARM 1 in the absence of tumor progression may continue maintenance with AM0010 alone at either 0.4 mg for patients weighing ≤ 80 kg or 0.8 mg for patients weighing > 80 kg after completion of FOLFOX or FOLFOX intolerance

Figure 8: ARM 2: FOLFOX Alone

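### The sentence beside the Arm 1 figures gives AM0010 maintenance at half the dose specified everywhere else

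*Protocol*

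**What the plan says.** The Protocol gives two different maintenance doses for Arm 1.

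**The lower pair, 0.4 mg (≤80 kg) or 0.8 mg (>80 kg).** Section 2.2, in the text with Figure 4, says that Arm 1 patients without progression "may continue maintenance with AM0010 alone at either 0.4 mg for patients weighing ≤ 80 kg or 0.8 mg" if heavier. The same sentence stands with the Arm 1 figure in the synopsis ("may continue maintenance with AM0010 alone at either 0.4 mg for patients weighing" and so on) and with Figure 7 in 5.1.3.

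**The higher pair, 0.8 mg (≤80 kg) or 1.6 mg (>80 kg), labelled 10 µg/kg.** The body text of 2.2 gives "either 0.8 mg patients weighing ≤80 kg or 1.6 mg for patients weighing >80 kg". The synopsis body text and Protocol 6.3.1 give the same amounts. Protocol 5.1.1 adds the injection volume: "either 0.8 mg in 0.2 mL for body weight" up to 80 kg, and 1.6 mg in 0.4 mL above it. SAP 6.3 repeats the pair, and SAP 10.1.1 plans twice the combination dose, 8 or 16 mg per two weeks.

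Two further places give the level without milligrams. Protocol 1.3.2 explains why 10 µg/kg "was chosen for the maintenance dose". The body text of 5.1.3 states 10 µg/kg "SQ qd (see Section 5.1.1").

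Protocol 6.3.1 allows maintenance reductions to 80% or 60%, made by giving fewer injections per week.

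**The concern.** This is an operative dosing instruction that contradicts itself by a factor of two, and a site could plausibly follow the wrong version:

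- The synopsis and 2.2 body text direct the reader to the display below for maintenance, which is where the wrong sentence sits.
- In 5.1.3, the dosing schedule, the figure sentence holds the only milligram amounts for maintenance. The correct amounts need a cross-reference to 5.1.1.
- The Schedule of Events (Appendix A) does not resolve it. Its AM0010 treatment row is marked for maintenance, but the attached footnote gives only the 5 µg/kg dose in two-week cycles.
- 0.4 or 0.8 mg is what the patient has been injecting during Cycles 1–12, so the error would look like ordinary continuation.

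At stake is two-fold underdosing in maintenance. Patients affected would be combined with full-dose patients in the maintenance exposure tables of SAP 10.1.1 and in the general safety tables of SAP section 12.

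**Working it through.** **Inputs.** Injection doses as listed above; 5 days on and 2 days off, so 10 injections per 14 days (Protocol 6.3.1); reductions to 80% and 60% by schedule (6.3.1); weight range 40–160 kg (the range of Table 9, stated in 1.3.2); 2.5 µg/kg as the dose that reaches the minimum trough and 20 µg/kg as the monotherapy MTD (1.3.2); 283 patients per arm (synopsis).

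**1. Reproduce the SAP's planned maintenance dose.** Dose per two weeks = 10 × injection dose.
- ≤80 kg: 10 × 0.8 = 8 mg
- >80 kg: 10 × 1.6 = 16 mg

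Both equal SAP 10.1.1.

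**2. The same calculation from the figure sentence.**
- ≤80 kg: 10 × 0.4 = 4 mg, and 4/8 = 50%
- >80 kg: 10 × 0.8 = 8 mg, and 8/16 = 50%

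**3. Could this be an allowed reduction?** The lowest level is 3 days on and 4 off, or 6 full-strength injections per 14 days: 6 × 0.8 = 4.8 mg and 6 × 1.6 = 9.6 mg. The figure sentence gives less (4 and 8 mg), and it halves the injection instead of changing the schedule. It is not a reduction level.

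**4. Dose per kilogram per injection.**

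| Weight | Figure sentence | Specified dose |
|---|---|---|
| 40 kg | 400/40 = 10 µg/kg | 800/40 = 20 µg/kg |
| 60 kg | 400/60 = 6.7 | 800/60 = 13.3 |
| 80 kg | 400/80 = 5 | 800/80 = 10 |
| 100 kg | 800/100 = 8 | 1600/100 = 16 |
| 160 kg | 800/160 = 5 | 1600/160 = 10 |

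Both columns stay above 2.5 µg/kg and do not exceed 20 µg/kg. The risk is underdosing, not overdose.

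**5. How many patients could be exposed to the error.** The documents give no expected number reaching maintenance. Assume exponential PFS and take the medians the Protocol quotes: 1.7 and 3.0 months for second-line FOLFOX (all patients, and ECOG 0–1; section 1.1.1) and 2.6 months for AM0010 plus FOLFOX in Phase 1b (1.3.2). Twelve cycles are 24 weeks: 168/30.4375 = 5.52 months. Progression-free fraction S = 2^(−5.52/median).

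| Median PFS | S at 24 weeks | Of 283 |
|---|---|---|
| 1.7 months | 0.105 | 30 |
| 2.6 months | 0.230 | 65 |
| 3.0 months | 0.279 | 79 |

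Patients who stop FOLFOX early for toxicity without progression would add to these counts.

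**6. Can the recorded data show which dose was given?** Protocol 5.1.3 says "The date, dose volume, and time of administration for each dose will be recorded" in the diary and on the CRF. AM0010 is "formulated at a concentration of 2 mg/mL and" 4 mg/mL (5.1.1). The specified 0.8 mg in 0.2 mL implies 4 mg/mL. A 0.4 mg dose would be 0.4/2 = 0.2 mL from the weaker strength or 0.4/4 = 0.1 mL from the stronger. The documents do not say which strength is used for 0.4 mg. If it is 2 mg/mL, volume alone would not separate the two doses.

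**The case against.** The best case for leaving this as a minor text correction is that the correct dose stands where dosing is actually instructed: 5.1.1, with volumes, and 6.3.1, the maintenance section. The synopsis and 2.2 state it shortly before the wrong sentence, and the three wrong sentences look like one error copied. Preparation details are in the Pharmacy Manual, which is not among the documents and may be right. Nothing shows that any site dosed from the figure sentence. That stands: the counts above are patients who could be affected, not patients known to be misdosed.

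The counts are also soft. Maintenance is optional. The 1.7-month median comes from 27 patients who included ECOG 2–3, and the 2.6-month median from 21 patients with a median of two prior therapies; this trial takes ECOG 0–1 after one prior regimen for metastatic disease.

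SAP 10.1.1 would show such patients at about 50% relative dose intensity in maintenance. They would therefore not be invisible, although a low intensity does not reveal its cause. The SAP plans no safety output for maintenance alone, so the mixing in safety concerns the general tables.

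Finally, Protocol 5.1.1 links 5–10 µg/kg to a survival benefit in Phase 1b. That was in combination with FOLFOX. The documents do not show the lower dose to be ineffective in maintenance, but it is half the dose chosen for it.

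These points limit the consequence. They do not remove the contradiction or the reason to correct it.

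**Conclusion.** The concern holds. Three sentences in the current Protocol give AM0010 maintenance at exactly half the specified dose in both weight groups, and no reduction rule in the Protocol permits that dose. The remaining statements agree with one another, so the intended dose, 0.8 or 1.6 mg, is not in doubt.

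The exposure is confined to Arm 1 patients who stop FOLFOX without progression: roughly 30 to 79 of 283 under the exponential assumption, before adding early stops for toxicity. How many would actually be misdosed cannot be derived from the documents. The primary OS test, the 393-event target and the alpha allocation do not depend on this. It should be fixed because it is a dosing instruction that is wrong as written, not because it threatens the primary analysis.

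**What to change.** Change the three figure sentences (synopsis, 2.2 with Figure 4, 5.1.3 with Figure 7) to 0.8 mg for ≤80 kg and 1.6 mg for >80 kg. Protocol 5.1.1, Protocol 6.3.1 and the SAP doses need no change. Send sites a letter stating the correct maintenance dose.

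From the recorded dosing data, identify any patient given 0.4 mg (≤80 kg) or 0.8 mg (>80 kg) per injection in maintenance. Read volume together with the strength dispensed. Flag these patients in the maintenance exposure tables and in the general safety tables.

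The cost is three text corrections, one site letter and a flag on data already collected. No extra patients or procedures are needed.
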